## 10.2 Study Endpoint Assessment

The details of the analyses will be provided in the statistical analysis plan (SAP). The following provides an overview of the planned analyses.

#### **10.2.1 PRIMARY ENDPOINT**

The primary endpoint is the level of stimulated c-peptide at 90-minutes derived from the mixed-meal tolerance test (MMTT) at 75±5 days following the first islet infusion. The difference in the means between the two treatment groups will be used as the measure of efficacy. Because the sample size is small, it is not practical to adjust for treatment center. The primary analysis will be based on an independent samples two-sided t-test. A difference will be declared statistically significant if  $p \le 0.05$ . The effect size will be estimated by the observed difference in the means for the two treatments. The estimated effect size and a 95% confidence interval for the effect size will be reported. If there is compelling evidence that the normal distribution does not hold then a logarithmic or square root transformation will be done before using the t-test. Appropriate adjustments will be made to compute the estimated effect size and its confidence interval.

The primary endpoint should be available in all randomized subjects. However, should a value not be available for a subject then a value will be imputed in one of two ways. If a value is observed for a subject after the 75 day period but before any subsequent islet infusion then that value will be used in the analysis. If no later value is available (e.g. the subject dies or withdraws from the study) then the lowest value observed for all subjects will be imputed for that subject. All imputations will be reported with the primary analysis. A secondary sensitivity analysis using multiple imputation methods will be performed to examine the effect of the choice of this imputation strategy.

#### **10.2.2 SECONDARY ENDPOINTS**

The secondary endpoints are defined in section 3.1.2.

HbA1c levels will be categorized for example, as either normal (<= 7.0 %), or non-normal (>7.0%). Dichotomous variables such as HbA1c (normal/non-normal) and rate of severe hypoglycemic events will be analyzed using logistic regression analysis with a term for treatment. Should a dichotomous endpoint not be evaluated for a particular individual then a failure will be imputed unless an evaluation is done at a time longer than 75 days after transplant and before an additional islet cell infusion, in which case that later value will be imputed.

Continuous variables such as QOL scales will be analyzed by a t-test. If there is compelling evidence that the normal distribution does not hold then a logarithmic or square root transformation will be done before using the t-test. If lack of normality persists, non-parametric tests will be used.

By examining multiple secondary endpoints it is likely that some variables will be found significantly different between the two treatment groups, but these findings may be Type I errors. Appropriate qualifiers will be reported with any significant secondary findings.

Regression models for longitudinal data (mixed models) will be used to examine the differences between groups in each of the response variables (HbA1c level and C-peptide levels) where measurements are repeated over time. Mixed models for dichotomous variables will be used to model full islet graft function over time. Survival analysis models will be used to compare time to becoming insulin dependent and to identify risk factors through Kaplan-Meier estimates and Cox regression models.

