### 1.2.3 Rational for Selection of Study Population

Iatrogenic hypoglycemia is a major unresolved problem for many patients with T1D. It is the limiting factor in the management of T1D, causing some deaths as well as recurrent physical, and recurrent (or even persistent) psychosocial, morbidity (Cryer, Fisher et al. 1994).

Neuroglycopenia can cause social embarrassment, and even lead to ostracism or be mistaken for disorderly or unlawful behavior(Cryer, Fisher et al. 1994). The more distressing the severe hypoglycemic episode, the greater the psychological fear of hypoglycemia(Irvine, Cox et al. 1992). The threat and fear of severe hypoglycemia can significantly discourage patients and health care providers from pursuing intensive insulin therapy and can therefore be a major but unrecognized impediment to achieving euglycemia(Irvine, Cox et al. 1991; Cryer, Fisher et al. 1994). Pramming et al. found that their patients were as concerned about the development of severe hypoglycemia as they were about the development of blindness or renal failure (Pramming, Thorsteinsson et al. 1991).

Ryan et al. documented the absence of episodes of severe hypoglycemia in 12 successful islet transplant recipients (median follow-up, 10.2 months) (Ryan, Lakey et al. 2001)whose diabetes was complicated by recurrent episodes of severe hypoglycemia pretransplant. This would suggest that hypoglycemia associated autonomic failure associated with defective counterregulation and impaired sympathodrenal responses is not just due to recurrent hypoglycemia. After a sustained period without any hypoglycemia most patients post islet transplant still had defective responses to hypoglycemia. The absence of clinically significant hypoglycemia post islet transplant despite the persistent defect in counterregulation in most subjects demonstrates the dominance of the absence of glucose regulated insulin secretion in the pathogenesis of severe hypoglycemia. Correction of this can only currently be attained with transplantation of beta cell tissue.

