### At 365 ± 14 days following the first and final islet infusion:

- The proportion of subjects with full islet graft function
- The proportion of subjects with an HbA1c <7.0% and free of severe hypoglycemic events from day 28 through day 365
- The percent reduction in insulin requirements

- HbA1c
- MAGE
- LI
- Clarke score
- HYPO score
- Basal (fasting) and 90-min glucose and C-peptide (MMTT)
- β-score
- C-peptide:glucose creatinine ratio
- Acute insulin response to glucose (AIRglu), insulin sensitivity, and disposition index derived from the insulin-modified frequently-sampled intravenous glucose tolerance (FSIGT) test
- Glucose variability and hypoglycemia duration derived from the continuous glucose monitoring system® (CGMS)
- The proportion of subjects receiving a second islet infusion
- The proportion of subjects receiving a third islet infusion

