## 8.2 Adverse Events 8.2.1 Collecting Procedure

AEs that are associated with a protocol-mandated procedure, that is not part of the normal standard of care, and hypoglycemic events will be collected beginning immediately after the consent document has been obtained. All other AEs will be collected immediately after randomization. All AEs will continue to be collected until study completion, or for 30 days after the subject prematurely withdraws from the study. AEs will be followed until the time the event is resolved, stabilized, or the participant completes or withdraws from the study, whichever occurs first.

AEs may be discovered through any of these methods:

- Observing the subject.
- Questioning the subject, this should be done in an objective manner.
- Receiving an unsolicited complaint from the subject.
- An abnormal value or result from a clinical or laboratory evaluation (e.g., a radiograph, an ultrasound, or an electrocardiogram) can also indicate an AE. If this is the case, then the evaluation that produced the value or result should be repeated until the value or result returns to normal or can be explained and the subject's safety is not at risk. If an abnormal value or result is determined by the investigator to be clinically significant, it must be reported as an AE.

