## 10.4 Sample Size and Power Calculations

The selected sample size is 18 subjects in each of the 2 arms. Historical data on 10 subjects from The University of Alberta suggest a standard deviation in the control group of approximately 0.9 nmol/L. Power calculations assumed that a two-sided 5% level t-test with equal variances would be used for the analysis. Based on a standard deviation of 0.9 nmol/L, this study will have 90% power to detect a difference of 1.0 nmol/L between the mean for the LMW-DS treatment group and the mean for the control group. The study will be able to detect a difference of 0.9 nmol/L with 80% power.

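### Section 10.2.2 treats the rate of severe hypoglycemic events as dichotomous without defining the yes/no variable, and names no method for an arm of 18 with no events

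*Protocol*

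**What the plan says.** Section 10.2.2 fixes both the type of variable and the model. It groups HbA1c and severe hypoglycemia together: "Dichotomous variables such as HbA1c (normal/non-normal) and rate of severe hypoglycemic events will be analyzed using logistic regression analysis with a term for treatment". HbA1c is given its two categories in the preceding sentence; severe hypoglycemia is given none. For missing data the same section says: "Should a dichotomous endpoint not be evaluated for a particular individual then a failure will be imputed". The exception is a later evaluation made before a further infusion, which is then used.

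Section 10.2.2 refers the reader to section 3.1.2 for the definitions of the secondary endpoints, but they stand in sections 4.1.2 and 4.1.3. The one efficacy endpoint there that uses severe hypoglycemic events is: "The proportion of subjects with an HbA1c <7.0% and free of severe hypoglycemic events from day 28 through day 365". No count or person-time rate of severe events is listed.

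On size, section 10.4 says: "The selected sample size is 18 subjects in each of the 2 arms". For non-normal continuous outcomes, section 10.2.2 names transformations and then non-parametric tests. For yes/no outcomes with empty cells it names nothing.

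**The concern.** A rate is ordinarily a number of events over time, which is not a yes/no variable and is not what logistic regression models. A reader of section 10.2.2 cannot tell which variable will be analysed, because the endpoint list has no item by that name.

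The second problem concerns the method. Ordinary logistic regression with one treatment term reproduces the 2×2 table. If one arm has no events, the fitted log odds ratio runs to infinity, and its standard error and Wald test carry no information. A clear difference between the arms could then be reported with a p-value near 1 and no usable interval.

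The outcome matters in this population. Every subject must have had a severe episode in the year before enrollment (section 3.1, criterion 6). The section on the rationale for the study population rests the acceptability of transplant risk largely on this harm. The data to analyse it well are already gathered, since "hypoglycemic events will be collected beginning immediately after the consent document has been obtained".

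**Working it through.** **Which variable is meant.** Three places bear on it.
- Section 10.2.2 puts the rate in a list of dichotomous variables.
- Section 4.1.3 defines only a per-subject yes/no composite.
- Section 10.3.2 uses rates for the share of patients with a condition.

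Together they favour reading the rate as the proportion of subjects with an event. Section 10.2.2 nevertheless names HbA1c and the event rate as two separate variables, so it does not plainly describe the composite either. The wording has to be settled.

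**The plan's own figure.** The protocol gives no expected risk or power for severe hypoglycemia. The 18 per arm come from the primary endpoint, for which historical data "suggest a standard deviation in the control group of approximately 0.9 nmol/L". With that SD, a difference of 1.0 nmol/L and a two-sided 5% t-test, the power is 89.9%, which agrees with the stated 90%. The size was therefore not chosen for a sparse binary outcome.

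**Chance of an empty arm.** Assume independent subjects with a common risk p of at least one severe event. For one arm, P(no events) = (1 − p)^18 = q. P(at least one empty arm) = 1 − (1 − q)².

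| Assumed p | q | At least one empty arm |
|---|---|---|
| 2% | 0.695 | 0.91 |
| 5% | 0.397 | 0.64 |
| 10% | 0.150 | 0.28 |
| 15% | 0.054 | 0.10 |
| 20% | 0.018 | 0.04 |

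For 5%: 0.95^18 = 0.397 and 1 − 0.603² = 0.64. Of this, 0.158 is the chance that both arms are empty, where no method can compare them, and 0.479 the chance that exactly one is. The figure exceeds one half only below a common risk of about 6.6%. With unequal risks it is 0.43 for 5% against 15% and 0.17 for 10% against 20%.

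**Effect of the imputation rule.** Suppose 5% of outcomes are missing (an assumption) and counted as failures. At p = 5% the failure probability is 1 − 0.95 × 0.95 = 0.0975. Then q = 0.9025^18 = 0.158, and the chance of at least one empty arm is 1 − 0.842² = 0.29 instead of 0.64.

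**The protocol's only count.** The rationale for the study population cites a report that "documented the absence of episodes of severe hypoglycemia in 12 successful islet transplant recipients". For 0 of 12, the one-sided 95% upper limit is 1 − 0.05^(1/12) = 22%, and the two-sided limit is 1 − 0.025^(1/12) = 26%. This count does not fix the risk.

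**What happens when one arm is empty.** For 0/18 against k/18:

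| k | Wald p | Likelihood-ratio p | Fisher p |
|---|---|---|---|
| 3 | 0.999 | 0.035 | 0.229 |
| 4 | 0.999 | 0.014 | 0.104 |
| 5 | 0.998 | 0.005 | 0.045 |
| 6 | 0.998 | 0.002 | 0.019 |
| 8 | 0.998 | 0.0003 | 0.003 |

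For k = 6 the fit stopped at a coefficient of about −21.9 with a standard error of about 11,360. Both only reflect where the iterations ended. Two checks for k = 6:
- Fisher: 2 × C(18,6)/C(36,6) = 2 × 18,564/1,947,792 = 0.019.
- Likelihood ratio: the log-likelihoods are −11.457 (separate arms) and −16.220 (pooled), so the statistic is 2 × 4.763 = 9.53 on 1 degree of freedom, p = 0.002.

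The Wald p stays near 1 whatever k is. For k = 3 or 4 the likelihood-ratio and Fisher tests fall on opposite sides of 0.05, so the choice of test decides the finding.

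**The case against.** The strongest defence is that a reader might infer more than the documents support, in four ways.

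- **That a true event rate is being forced into a yes/no model.** Section 4.1 defines no count or person-time rate, and the protocol elsewhere uses rates for proportions of patients. The evidence points to loose wording, not to a count analysed wrongly. This part of the defence stands.
- **That an empty arm is the likely result.** No expected risk is stated. The 0 of 12 concerns successful recipients only, whereas this trial will include partial function and graft failure. Imputed failures make an empty event cell rarer, and HbA1c failures make it rarer still for the composite. The 0/18 against 6/18 table shows how the statistic behaves; it does not forecast the result. At a common risk of 5%, exactly 6 events in 18 has probability 18,564 × 0.05^6 × 0.95^12 ≈ 0.0002. This also stands, so an empty arm should be called realistic, not likely.
- **That logistic regression as such fails.** Only the odds ratio and the Wald test do. Likelihood-ratio and exact tests remain usable, section 10.2 calls itself an overview, and the SAP may choose the test. This stands in part. The protocol itself fixes logistic regression for this variable, and it provides a fallback for continuous data but none here.
- **That repeated events go unexamined.** The HYPO score, a listed endpoint, draws on all severe episodes recalled over the previous 12 months, and CGMS records the number and duration of hypoglycemic episodes. Event burden is not ignored.

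**Conclusion.** The point holds in limited form. Section 10.2.2 names a variable that section 4.1 does not define, calls it dichotomous without stating the two categories, and assigns it a model whose odds ratio and Wald test give no usable answer if one arm has no events. The chance of at least one empty arm runs from 64% at an assumed 5% common risk to 28% at 10% and 4% at 20%. An assumed 5% of outcomes missing and counted as failures lowers the 64% to 29%. All these risks are assumptions, and subjects are taken as independent.

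The documents do not show that a person-time rate is being misanalysed, nor that an empty arm is more likely than not. The matter concerns a secondary endpoint; the primary analysis is unchanged. It is worth correcting because the correction is nearly free and the outcome is central to the rationale for transplanting these patients.

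**What to change.** In section 10.2.2:

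1. Replace the rate of severe hypoglycemic events with *any severe hypoglycemic event, day 28 through day 365 (yes/no)*. Align this with section 4.1, either by listing it there as a component of the composite or by stating that the composite is the variable analysed. Correct the cross-reference from section 3.1.2 to sections 4.1.2 and 4.1.3.
2. For sparse yes/no endpoints, use an exact test with an exact confidence interval for the risk difference, or Firth-penalized logistic regression with profile-likelihood intervals, in place of ordinary logistic regression. Choose one of the two before the data are seen.
3. Only if an event count is really intended, list it as an endpoint in section 4.1 and use a count model with a person-time offset. Such a model also lacks a finite rate ratio when an arm has no events, so it too needs an exact or permutation fallback.

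The cost is wording in the protocol or SAP. Hypoglycemic events are already collected, so no new data are needed. The drawback is that exact tests are slightly conservative.

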### 4. STUDY DESIGN

This is an open label, stratified, randomized, multi- center study that will be conducted in 7 centers in Scandinavia (Norway, Sweden, Finland, and Denmark).

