#### 7. STUDY PROCEDURES 7.1 Enrollment and Screening

The site investigator or designated study personnel will explain the research study in lay terms and discuss available modes of treatment individually with every potential study patient referred to the Nordic Network for Clinical Islet Transplantation. If the patient is willing to participate and once the written consent is obtained, the subject is enrolled and the screening period begins. Patients who have been previously assessed for standard islet and/or pancreas transplantation at the participating sites may ultimately be enrolled in this trial and, as a result, may have some testing done prior to signing the consent document.

Enrollment into the study is done using an electronic internet entry system that can be accessed using any computer connected to the Internet. Authorized personnel will be required to log into the system using their assigned user identification and password. Allocation to a unique subject identification number is computer generated and assigned at the time of enrollment.

Subject eligibility will be confirmed through the performance of the screening visit procedures detailed in the Schedule of Events (Appendix 1). More than one visit may be necessary to complete all of the screening procedures. Results from assessments completed prior to signing informed consent, must be current within the windows stated in the table below.

Screening Assessments	Allowable timeframe prior to the date of consent
EBV IgG	No limit. Positive test result required for eligibility.
Retinopathy evaluation; Physical exam; Chest x-ray; Abdominal Ultrasound; ECG; Myocardial Scintigram; Conduction Velocity and RR intervals; Serology (HIV, Hepatitis B, Hepatitis C); CMV IgG and IgM; Coagulation Status (APTT, PK, fibrinogen, platelets)	Within one year
CBC w/ differential; Serum Chemistry Panel and CRP; Urine Albumin; Fasting Lipid Profile (Total, LDL, HDL, Triglycerides); GFR	Within 6 months
Quality of Life Questionnaires; Medial and Diabetes History Assessment; Panel Reactive Antibody (Alloantibodies); Record recipient HLA and Blood Type; Pregnancy Test; HBA1c; MMTT; FSIGT; LI; HYPO; Clarke Score; c-peptide to Glucose Creatinine ratio; Serum to Archive; PBMC and Plasma to Archive; RNA to Archive.	After informed consent has been obtained

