## 7.2 Waiting List / Baseline Visit

During the period when the subject is awaiting for their first transplant, they will return to the study site for clinic visits every 6 months. Waitlist assessments will be repeated at pre-defined intervals as detailed below. Results from assessments done closest to the date of randomization will be used as the subject's baseline values.

Waitlist Assessments	Timetable for repeat testing while on the waiting list
Retinopathy Evaluation; Physical Exam; Chest x-ray; ECG; Coagulation Status (APTT, PK, fibrinogen, platelets); CGMS; Serology (HIV, Hepatitis B, Hepatitis C	Once a Year
CBC with differential; Serum Chemistry Panel; Glycemic Lability- LI ( repeat only if used as inclusion criteria); Glycemic Lability (MAGE); Alloantibodies; Quality of Life Questionnaires (SF36, DTSQ); HbA1C; Blood Sugar Records and Hypo sheets; Full Hypo Score; Clarke Score.	Once every 6 months
Baseline Assessments	
Re-evaluation of the eligibility criteria; Record concomitant medications; CMV and EBV by PCR; Autoantibodies; RNA and Plasma to Archive; Alloantibodies; Physical Exam; CBC with differential; Serum Chemistry Panel; Coagulation Status (APTT, PK, fibrinogen, platelets); Blood Sugar Records and/or Hypo sheets; Serology (HIV, Hepatitis B, Hepatitis C); Chest x-ray; ECG; Cross Match; Serum Pregnancy Test; HbA1C	At the time the pancreas becomes available, prior to transplant

Table 3. Baseline/Waiting List Assessment Windows

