## 7.3 Randomization and Study Treatment Schedule

Once a compatible islet prep becomes available, then the site personnel will re-confirm the eligibility criteria. Eligible subjects will be randomized (1:1), to the experimental arm or control arm. A total of 36 subjects will be randomized; 18 subjects to an experimental arm and 18 subjects to a control arm.

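### Continuous secondary endpoints with a recorded pre-transplant value are compared by an unadjusted t-test; ANCOVA on that baseline would usually give narrower intervals for one degree of freedom

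*Protocol*

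**What the plan says.** Section 10.2.2 gives the between-arm method: "Continuous variables such as QOL scales will be analyzed by a t-test". Its fallbacks are a logarithmic or square root transformation, then non-parametric tests. Mixed models are also planned for HbA1c and c-peptide over time, with covariates not stated.

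Pre-transplant values exist. Section 7.1 (Table 2) lists, among the screening tests, "HBA1c; MMTT; FSIGT; LI; HYPO; Clarke Score". Section 7.2 (Table 3) adds MAGE, CGMS and SF36 on the waiting list and settles which value is baseline: "Results from assessments done closest to the date of randomization will be used".

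For the primary endpoint, Section 10.2.1 specifies an independent-samples t-test and gives one reason against adjustment, which concerns center only: "Because the sample size is small, it is not practical to adjust for treatment center".

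On the randomization, Section 4 states: "This is an open label, stratified, randomized, multi- center study that will be conducted in 7 centers in Scandinavia". Section 7.3 says only "Eligible subjects will be randomized (1:1), to the experimental arm or control arm", and Section 7.8.1 describes the web-based system. Neither names a stratification factor.

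**The concern.** Where a variable is measured in the same form before and after transplant, part of its spread at follow-up is usually difference between subjects that was already present at baseline. A two-sample t-test leaves that spread in the error term; ANCOVA removes it. With 36 subjects the intervals for the secondary endpoints will be wide, so the loss can matter for estimates meant to support the primary result.

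The small-sample reason in Section 10.2.1 concerns center, where seven sites need six terms. It does not carry over to a single baseline covariate, and Section 10.2.2 gives no reason of its own.

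The word stratified raises a smaller matter. If a factor was used, the analysis should name it and account for it. If none was used, the word is wrong.

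**Working it through.** **Inputs from the protocol.** Section 10.4: "The selected sample size is 18 subjects in each of the 2 arms", SD 0.9 nmol/L for the primary endpoint, and "Power calculations assumed that a two-sided 5% level t-test with equal variances would be used for the analysis". Allocation is 1:1 (Section 7.3). The baseline-to-follow-up correlation ρ is not given, so it is assumed and varied.

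**Step 1: the plan's own figure.** Exact noncentral-t power for a difference of 1.0 nmol/L, SD 0.9, 18 per arm and 34 df is 0.899. The stated 90% reproduces.

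**Step 2: unadjusted interval.** The 95% half-width in SD units is t(0.975, 34 df) × √(2/18) = 2.032 × 0.333 = 0.677.

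**Step 3: ANCOVA interval.** One covariate leaves 33 df. The expected variance factor, including the penalty for chance baseline imbalance, is V = (1 − ρ²)(1 + 1/32). The half-width is t(0.975, 33 df) × √(2/18 × V), with t = 2.035. The equivalent sample size is 36/V.

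| Assumed ρ | V | Half-width (SD) | Relative to t-test | Equivalent N |
|---|---|---|---|---|
| 0 | 1.031 | 0.689 | 1.02 | 35 |
| 0.3 | 0.938 | 0.657 | 0.97 | 38 |
| 0.5 | 0.773 | 0.596 | 0.88 | 47 |
| 0.7 | 0.526 | 0.492 | 0.73 | 68 |

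Setting the two half-widths equal gives a break-even of ρ ≈ 0.18.

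**Step 4: simulation check.** In 20,000 simulated trials of 18 per arm, mean width ratios were 1.02, 0.97, 0.88 and 0.73 at ρ = 0, 0.3, 0.5 and 0.7. Type I error was about 5% for both methods. Power for a 1-SD difference was 83% unadjusted, against 85%, 91% and 98% with adjustment at ρ = 0.3, 0.5 and 0.7.

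**Step 5: if the t-test is on change scores.** Its width relative to a follow-up-only t-test is √(2(1 − ρ)): 1.18, 1.00 and 0.77 at ρ = 0.3, 0.5 and 0.7. ANCOVA (0.97, 0.88, 0.73) is narrower each time.

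**Step 6: the primary endpoint.** Section 3.1 requires stimulated c-peptide below 0.099 nmol/L at entry. The baseline SD is then at most 0.099/2 = 0.0495 nmol/L, or 0.099/√12 = 0.029 if values are evenly spread. With ρ = slope × baseline SD / 0.9, a slope of 1 gives 0.03 to 0.06. A slope of 5 with even spread gives 0.16, still below break-even.

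**Step 7: center terms.** Counting only the lost df (28 instead of 34), power for 1.0 nmol/L falls from 0.899 to 0.896 if centers explain nothing. That requires arms balanced within every center, which the protocol does not promise. With allocation not stratified by center, 36 subjects spread evenly or at random over 7 centers, and six center terms, average power is about 0.83, 0.87 and 0.90 if centers explain 0%, 10% and 20% of the variance (assumed).

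**The case against.** The strongest reply has four parts.

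- **The t-test is valid.** This stands: nothing is biased, the endpoints are secondary, and Section 10.2.2 already promises qualifiers on significant findings.
- **The gain depends on an unknown correlation.** This also stands. Entry selects for extreme Clarke, HYPO or LI values and caps HbA1c at 10%, and the transplant is meant to change these measures, so high correlations cannot be presumed. The stakes are lopsided, though: about 2% wider at worst, against 12% to 27% narrower at 0.5 to 0.7.
- **Baseline is partly used already.** Percent reduction in insulin contains it, HbA1c also gets a mixed model, and Section 4.1.2 compares quality of life with screening. Section 10.2.2 does not say whether the t-test is on follow-up or change; on change, ANCOVA is still narrower (step 5).
- **Section 10.2 is an overview and leaves details to the SAP, which is not at hand.** The SAP may name covariates. The t-test is nevertheless a stated choice, not a gap.

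A reader might go further and infer that the primary analysis should be adjusted too. The documents do not support this. Its baseline has almost no spread (step 6). Center adjustment could lose power unless centers explain roughly 20% of the variance or were strata (step 7), so declining it is a defensible trade-off. Nor can one say that the intervals mismatch the randomization scheme, because no factor is named. GFR does not belong on the list either: Section 4.1.4 treats its reduction as an adverse-event item.

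**Conclusion.** The point holds for continuous secondary endpoints with a same-form pre-transplant value: HbA1c, LI, MAGE, HYPO, Clarke score, CGMS measures and SF36. The planned test is sound but inefficient once the correlation exceeds about 0.18. The size of the loss rests on assumed correlations, a roughly linear baseline relation, and complete data on 18 subjects per arm. It does not touch the primary endpoint or the validity of any test. The unexplained word stratified is a real but minor inconsistency, and its effect cannot be quantified without a named factor.

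**What to change.** **Section 10.2.2:** analyze each continuous secondary endpoint that has a same-form baseline by ANCOVA on the follow-up value, with terms for treatment and baseline. Use the pre-randomization value defined in Section 7.2, not the repeat baseline visit that Section 7.7 starts before a further transplant, which falls after randomization. Except DTSQc, a change questionnaire whose screening counterpart is the DTSQs. Keep the existing transformation and non-parametric fallbacks.

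**Section 10.2.1:** leave the primary c-peptide t-test without baseline or center adjustment.

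**Section 4 against Sections 7.3 and 7.8.1:** delete the word stratified if no strata were used. If a factor was used, name it and include it in the analysis.

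**Cost:** one degree of freedom per endpoint, and no new data or visits. The wording changes fall in the protocol as well as the SAP. Section 10.7 requires an amendment, with DSMB, sponsor and health-authority review, if they count as changes to principal features. They should be settled before outcome data by arm are examined.
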